10.5 Statistical Methods

10.5.1 Efficacy Analyses

The primary population for efficacy analyses will be the MITT population (see Section 10.4). Efficacy analyses will also be performed on the ITT and the PP populations and will be considered supportive.

The primary analysis will be conducted once Enrollment A is complete.

The number and percent of subjects who demonstrate a positive outcome for the primary efficacy outcome as well as all secondary and tertiary efficacy outcomes will be presented.

The primary endpoint, defined as the percentage of subjects at the Test of Cure Visit with “therapeutic cure”, will be compared between groups using a chi-square test with a 2-sided significance level of 0.05.

The secondary endpoints will be analyzed analogously to the primary endpoint.

In Enrollment A in cases of bilateral otomycosis, if only 1 ear has a positive fungal culture at Screening/Baseline, that ear will be used as the study ear for efficacy analyses. If both ears have a positive fungal culture at Screening/Baseline, the ear with the worse infection at Screening/Baseline, as assessed by the investigator by taking into account clinical signs and symptoms, will be used as the study ear for efficacy analyses. If both ears have a positive fungal culture at Screening/Baseline and are determined by the investigator to have the same degree of infection at Screening/Baseline, the left ear will be used as the study ear for the purposes of efficacy analyses.

Descriptive statistics will be provided for otomycosis signs and symptoms and also for clinical cure, modified therapeutic cure, and therapeutic improvement; each at Day 15 will be summarized using the ITT population for both the Randomization Period and the Optional Open-label Extension.

10.5.1.1 Multiple Comparison/Multiplicity

The overall Type I error will be controlled by requiring the primary efficacy endpoint to be statistically significant. Specifically, failure of the primary efficacy endpoint will invalidate the statistical significance of the secondary efficacy endpoints.

Evaluation of the secondary efficacy endpoints will use a gated sequential procedure in order to control for multiplicity. These tests will be performed for only the MITT population. The testing process will terminate whenever a statistical test for a step is not significant, i.e., any subsequent test will be considered not significant. The order of testing is:

1. Percentage of subjects with mycological cure at the Test of Cure Visit.
2. Percentage of subjects with clinical cure at the Test of Cure Visit.

10.5.2 Safety Analyses

Safety summaries will be conducted using two safety populations (see Section 10.4.4). All AEs occurring during the study will be recorded and classified using terminology from the Medical Dictionary for Regulatory Activities (MedDRA). All reported treatment-emergent adverse events (TEAEs), defined as any AE with an onset on or after the date of first study drug application, will be summarized. Summaries will provide the number of subjects reporting TEAEs, system organ class, preferred term, severity, and relationship to study drug. When summarizing TEAEs by severity or relationship to study drug, each subject will be counted only once within a system organ class or a preferred term using the event with the greatest severity or causality, respectively, within each category. All reported SAEs will be summarized by the number of subjects reporting the event, system organ class, preferred term, severity, and relationship to study drug.

Summaries will be provided separately for the blinded and unblinded portions. Specifically, summaries will be provided by treatment group for the Randomization Period using the Randomization Period safety population, and for all open-label subjects using the Open Label safety population.

All information pertaining to AEs noted during the study will be listed by study portion (Enrollment A or Enrollment B), study period (Randomization or Optional Open-label), as applicable, treatment group, and subject and will include a verbatim description of the event as reported by the investigator, as well as the preferred term, system organ class, start date, stop date (if stopped), seriousness, severity, action taken regarding the study drug, corrective treatment, outcome, and relationship to the study drug. In addition, a listing of subjects who prematurely discontinue from the study due to AEs will be provided as well as a listing of subjects who report an SAE.

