
groups for the secondary endpoints of clinical cure and mycological cure. Missing data will be imputed as treatment failures for the primary and secondary efficacy analyses; missing data otherwise will not be imputed.
 
The primary population for efficacy analyses will be the MITT population, defined as all subjects who were randomized with a positive fungal culture at Screening/Baseline.
 
Two safety populations will be used for safety analyses. The first will be the Randomization Period safety population, defined as all subjects who received at least one dose of study drug and had at least one post-Baseline safety assessment during the Randomization Period; this population will be used for safety data for the Randomization Period. The second will be the Open Label safety population, defined as all subjects who received at least one dose of miconazole oil and had at least one post-Baseline safety assessment during the Optional Open-label Extension or Enrollment B; this population will be used for safety data for the Optional Open-label Extension and Enrollment B.
 
All AEs occurring during the study will be recorded and classified using terminology from the Medical Dictionary for Regulatory Activities (MedDRA). All reported TEAEs, defined as any AE with an onset on or after the date of first study drug application, will be summarized. Summaries will provide the number of subjects reporting TEAEs, system organ class, preferred term, severity, and relationship to study drug. When summarizing TEAEs by severity or relationship to study drug, each subject will be counted only once within a system organ class or a preferred term using the event with the greatest severity or causality, respectively, within each category. All reported serious AEs (SAEs) will be summarized by the number of subjects reporting the event, system organ class, preferred term, severity, and relationship to study drug. Descriptive statistics will be presented for all safety data.

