3.1.2 Optional Open-label Extension

Subjects who either complete the Randomization Period of the study (up through the Test of Cure Visit), or who are prematurely discontinued from study treatment during the Randomization Period due to worsening of signs and/or symptoms of otomycosis in the judgment of the investigator, will be offered the opportunity to participate in an optional open-label extension, if they have a visual presence of fungal elements in at least one ear treated during the Randomization Period. Only the ear(s) that were treated in the Randomization Period will be potentially eligible for treatment during the Optional Open-label Extension.

All subjects in the Optional Open-label Extension will receive miconazole oil for 14 days. No unblinding of the subject's treatment in the Randomization Period will occur at this time.

Before a subject enters the Optional Open-label Extension, all procedures for the Test of Cure Visit will be completed for that subject; however, a fungal culture will not be required at this visit for subjects known to have a negative fungal culture at Screening/Baseline, as assessed after at least 14 days of incubation by the clinical laboratory performing the fungal culture.

At the first visit of the Optional Open-label Extension (Day OLE1, which will occur while the subject is already onsite for the Test of Cure or Early Termination Visit from the Randomization Period), study drug (miconazole oil) will be weighed and dispensed to the subject along with a subject diary. Subjects or their caregivers will administer the first dose of miconazole oil at the site. AEs and concomitant medications will then be assessed. Subjects will then continue to administer miconazole oil and to complete the subject diary twice per day for a total of 14 days, following the same instructions as provided at the Screening/Baseline Visit on Day 1.

Subjects will return to the clinic on Day OLE15 for the End of Treatment Visit, at which time a clinical evaluation of the signs and symptoms of otomycosis will be performed, as well as an assessment of AEs and concomitant medications. A urine pregnancy test will be performed in women of childbearing potential. The subject will return all unused miconazole oil along with the completed subject diary.

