6 STUDY SCHEDULE

6.1 Enrollment A

6.1.1 Study Flow Chart

The study schedule for Enrollment A is presented in Table 3.

Table 3 Study Schedule: Enrollment A

Evaluations and Procedures:	Randomization Period				Optional OLE	
	Screen/ Baseline ^a Day 1	On Treat ^b Day 8	End of Treat ^b Day 15	Test of Cure ^c Day 22 ^d	Start of Treat Day OLE1 ^e	End of Treat Day OLE15 ^b
Informed consent/assent	X					
Inclusion/exclusion criteria	X					
Medical/medication history	X					
Physical examination	X					
Otomycosis signs and symptoms	X	X	X	X		X
Urine pregnancy test ^f	X			X		X
Randomization	X					
Dispensation of study drug	X				X	
Dispensation of subject diary	X				X	
Collection of subject diary		X ^g	X			X
Administration of study drug at site	X				X	
Weighing of study drug	X	X	X		X	X
Collection of study drug			X			X
Fungal culture ^h	X		X	X		
Ear cleaning	X	X				
AE evaluations	X	X	X	X	X	X
Concomitant medications review	X	X	X	X	X	X

- a. Procedures for this visit may occur over a 2-day period, if necessary (with Day 1 defined as the first day on which study drug is administered). All procedures for this visit must occur before the first administration of study drug with the exceptions that AE evaluations and review of concomitant medications will also occur after the start of study drug on Day 1.
- b. This visit may occur up to 3 days later than the specified day.
- c. This visit may occur up to 1 day sooner or up to 8 days later than the specified day.
- d. In case of early termination, the assessments planned for the Test of Cure Visit should be performed with the exception of fungal culture, which is not required.
- e. This visit will occur on the same day as the final visit of the Randomization Period.
- f. Females of childbearing potential only.
- g. The subject diary will be returned to the subject after review by study staff for documentation of missed and/or extra study drug doses.
- h. Samples will be used for growth and identification of fungal organisms as well as susceptibility testing to miconazole. Fungal cultures are not required to be taken at Day 15 or at Day 22 for subjects known to have a negative fungal culture at Screening/Baseline (assessed after at least 14 days of incubation by the clinical laboratory performing the fungal cultures).

OLE=Open-label Extension; Screen=Screening; Treat=Treatment

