10.1.4 Safety Endpoint

A safety endpoint will be the percentage of subjects with treatment-emergent AEs (TEAEs), with treatment-emergent defined as occurring upon or after administration of the first dose of study drug.

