10.4.4 Safety Population

Two safety populations will be defined.

The Randomization Period safety population will include all subjects who received at least one dose of study drug and had at least one post-Baseline safety assessment during the Randomization Period.

The Open Label safety population will include all subjects who received at least one dose of miconazole oil and had at least one post-Baseline safety assessment during the Optional Open-label Extension or Enrollment B.

Safety analyses for the Randomization Period will be performed using the Randomization Period safety population. Safety analyses for the Optional Open-label Extension and Enrollment B will be combined and presented using the Open Label safety population.

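### Treatment-emergent AEs are counted from the date of first application in the synopsis and Section 10.5.2 but from the first dose in Section 10.1.4; separately, Section 8.1.1 has a minor SAE wording conflict

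*Combined protocol and SAP*

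**What the plan says.** **Treatment-emergent definition.** The synopsis (Statistical Analyses) has "TEAEs, defined as any AE with an onset on or after the date of first study drug application", and Section 10.5.2 repeats that definition: "defined as any AE with an onset on or after the date of first study drug application". Section 10.1.4, which sets out the only named safety endpoint, has "with treatment-emergent defined as occurring upon or after administration of the first dose of study drug".

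**Collection and timing.** Section 8.4 starts AE collection at informed consent and lists onset as a date. Sections 6.1.2.1, 6.1.3.1 and 6.2.2.1 tell sites to report whether AEs on Day 1, Day OLE1 and Day B1 came before or after the first dose. Footnote a of Tables 3 and 4 places all Day 1 and Day B1 procedures ahead of that dose, except that AEs and medications are also reviewed after it.

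**Periods.** Section 10.5.2 states: "Summaries will be provided separately for the blinded and unblinded portions". Section 10.4.4 states: "Safety analyses for the Optional Open-label Extension and Enrollment B will be combined and presented using the Open Label safety population". On Day OLE1, Table 3 footnote e says: "This visit will occur on the same day as the final visit of the Randomization Period". Section 3.1.2 adds: "Before a subject enters the Optional Open-label Extension, all procedures for the Test of Cure Visit will be completed for that subject".

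**Serious events (separate item).** Section 8.1.1 gives, as examples of serious important medical events, allergic bronchospasm treated intensively in an emergency room or at home, and convulsions or blood dyscrasia without inpatient admission. Its closing sentence says, with no stated exception, that emergency treatment as an outpatient without admission does not make an SAE.

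**The concern.** A calendar date and a dosing time are different start points whenever something happens on the dosing day before the dose. The protocol makes that window real: the subject has consented, is examined, has a culture taken and, on Day 1 of Enrollment A, has the ear cleaned before the first drops go in. Section 5.1.1 allows oral analgesics for pain from such procedures, so pain that starts after cleaning and before dosing is a plausible recorded AE. Two programmers working from the same database, one following Section 10.1.4 and the other Section 10.5.2, could report different values for the one named safety endpoint. The date version would also put events under a treatment the subject had not yet received.

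The Section 8.1.1 item has a different consequence. The 24-hour reporting duty in Section 8.4.1 depends on whether an event is an SAE, and an investigator reading Section 8.1.1 can find two answers for the same event.

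**Working it through.** **1. Which events the two definitions classify differently**

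| Onset of AE | Date rule (synopsis, 10.5.2) | Dose rule (10.1.4) |
|---|---|---|
| Day before first dosing day | Not treatment-emergent | Not treatment-emergent |
| First dosing day, before the dose | Treatment-emergent | Not treatment-emergent |
| First dosing day, after the dose | Treatment-emergent | Treatment-emergent |
| Later day | Treatment-emergent | Treatment-emergent |

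Only the second row differs. Every event counted by the dose rule is also counted by the date rule, so the date rule can add events but cannot hide any. If screening is spread over two days, as Section 6.1.2.1 permits, pain that starts on the earlier day is excluded by both rules. The ear-cleaning example applies to Day 1 only, because no cleaning is scheduled at Day OLE1 or in Enrollment B.

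**2. Size on planned numbers (Section 3.4.2)**

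Inputs: 220 subjects randomized 1:1, so 110 per arm; 55 vehicle subjects projected to enter the extension; 170 subjects in Enrollment B.

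- Randomized arm: 1/110 = 0.0091, or 0.91 percentage points per reclassified subject.
- Open-label table: 55 + 170 = 225, and 1/225 = 0.0044, or 0.44 points per reclassified subject.

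Both are maxima on these denominators. A subject who has another treatment-emergent AE in the same period does not change the percentage at all. The 225 leaves out any active-arm subjects who enter the extension, for whom the protocol gives no projection; including them would lower the 0.44. The documents give no rate of pre-dose events on the dosing day, so the number of subjects affected cannot be estimated.

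**3. Day OLE1**

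This day is shared with the final randomized visit, so the passages need to be read together. Section 8.4 runs AE collection for the Randomization Period through the Test of Cure Visit. Section 3.1.2 requires that visit's procedures to be finished before extension entry and places the OLE1 AE assessment after the first open-label dose. Table 3 schedules separate AE evaluations for the two visits. Section 6.1.3.1 asks for before/after-dose timing. Together these imply that an AE found before the first open-label dose belongs to the Randomization Period. No single sentence in the analysis sections says so.

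**4. Section 8.1.1**

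Take a bronchospasm treated intensively in an emergency room without admission. Under the example in the important-medical-event bullet it is serious. Under the closing sentence, read literally, it is not. The same holds for a convulsion treated as an outpatient emergency without admission.

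**The case against.** The strongest reply is that this is a wording mismatch with little consequence. It touches only events in a short window on one day, safety is descriptive, and both randomized arms go through the same pre-dose procedures, so the difference between arms should hardly move. Sites must already record the timing that resolves the matter, and Section 10 leaves full details to a separate statistical analysis plan that is not in the text supplied. Most of this stands and is why the point is minor. It does not remove the mismatch: a later plan would inherit two definitions and would have to overrule one of them.

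Two stronger readings are tempting, and the documents do not support either.

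- A reader might infer that nothing governs AEs dated Day OLE1, so that a vehicle subject's pre-dose event could be tabulated as a miconazole event. That would need a date-only rule restarted at Day OLE1, and no section states one. Sections 3.1.2 and 8.4 and Table 3 point the other way.
- A reader might infer that the AE listing in Section 10.5.2 leaves out the before/after-dose item, because it names "start date, stop date (if stopped), seriousness, severity, action taken regarding the study drug, corrective treatment, outcome, and relationship to the study drug" among its contents. The sentence covers all AE information and says what the listing will include. It is not an exhaustive specification, and the eCRF is not supplied.

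On Section 8.1.1, the closing sentence sits beside an exclusion for elective or preplanned hospitalization and is probably meant to limit only the hospitalization criterion. That is the likely intent, but the sentence does not say so.

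**Conclusion.** The inconsistency is real and is in the current text: the one named safety endpoint has two start points. Its severity is minor. Each affected subject is worth at most 0.91 points in a randomized arm or 0.44 points open-label, assuming the planned numbers of Section 3.4.2 and no other treatment-emergent AE in that subject in the same period. How many subjects would be affected is unknown. Absolute rates would move more than the contrast between arms, and the direction is known, since the date rule gives a percentage equal to or higher than the dose rule. For Day OLE1 the documents already imply the right assignment, so a confirming sentence is enough.

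The Section 8.1.1 conflict is a separate minor item. It has no rate attached, such events should be rare, and it has no bearing on the size of the treatment-emergent point.

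**What to change.** 1. Replace the date-based definition in the synopsis and Section 10.5.2 with the dose-based one of Section 10.1.4, and state that first-dosing-day events are classified by the before/after-first-dose timing reported under Sections 6.1.2.1, 6.1.3.1 and 6.2.2.1. What matters most is a single definition. The dose-based one is preferable because it already belongs to the endpoint and keeps pre-dose events out of the treatment-emergent count.
2. Add one sentence to Section 10.5.2 confirming that events on Day OLE1 before the first open-label dose stay in the Randomization Period.
3. Separately, reconcile the statements in Section 8.1.1 so that the closing sentence limits only the hospitalization criterion and does not override the other seriousness criteria.

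The cost is a few sentences and slight extra programming. Sites are already told to report the timing. Whether the eCRF has a field for it cannot be seen from the documents, so one may have to be added.

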10.5.3 Subject Demographics and Baseline Characteristics

Subject demographic and baseline characteristics will be summarized descriptively for the MITT, PP, and safety populations and will be supported with individual subject data listings.

10.5.4 Missing Data

Missing data will be imputed as treatment failures for the primary and secondary efficacy analyses.

Missing data otherwise will not be imputed.

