5.1.2 Prohibited Medications

Other than the study drug, no other topical medications (including but not limited to antibiotics, alcohol, boric acid, peroxide, and/or corticosteroids) are allowed to be used in the ear(s) being treated with study drug. Other prohibited treatments include systemic antifungal therapy, warfarin, immunosuppressive or immune-stimulating drugs, and systemic steroids. A subject who discontinues study drug during the Randomization Period and who subsequently uses a topical corticosteroid (e.g., to treat an AE such as itching) in the ear(s) that were treated with study drug during the Randomization Period will be eligible for the Optional Open-label Extension if the topical corticosteroid is discontinued in the ear(s) that will be treated with study drug before the start of study drug in the Optional Open-label Extension, and as long as the subject meets all other eligibility criteria for the Optional Open-label Extension.

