10.1 Study Endpoints

10.1.1 Primary Efficacy Endpoint

The primary efficacy endpoint will be the percentage of subjects at the Test of Cure Visit with "therapeutic cure", defined as "mycological cure" plus "clinical cure" for the study ear, at the end of the Randomization Period for each subject. Mycological cure is defined as a negative mycological culture, and clinical cure is defined as the absence of all otomycosis signs and symptoms based on investigator assessment according to the scales for each individual sign or symptom. See Section 7.4 for the scales for each otomycosis sign and symptom.

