10.4.2 Modified Intent-to-treat Population

The modified intent-to-treat (MITT) population will be a subset of the ITT population. The MITT population will include subjects in the ITT population with a positive fungal culture at Screening/Baseline. The MITT population will be the primary population to assess efficacy.

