10.4.3 Per Protocol Population

The per protocol (PP) population will be a subset of the MITT population and will include all subjects who complete the Test of Cure visit without any major protocol violations. The PP population will include subjects in the MITT population who did not meet any of the following criteria:

- Violated the inclusion/exclusion criteria
- Used an interfering concomitant medication
- Did not attend the Test of Cure visit
- Did not attend the End of Treatment visit
- Have not been compliant with the dosing regimen (i.e., subjects must have received 80%-120% of the expected applications of study medication in the study ear during participation in the study)
- Out of visit window at the Test of Cure Visit (-1/+8 days)

Subjects who discontinue from the study due to an adverse event related to study treatment, documented lack of treatment effect, or worsening of condition will be included in the PP population. Prior to breaking the blind, other additional criteria may be added to the list to accommodate for unforeseen events that occurred during the conduct of the trial that result in noteworthy study protocol violations.

All efficacy analyses will be performed using the PP population in a supportive manner.

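### The primary analysis turns only missing outcomes into failures, so a subject who used prohibited therapy but has complete, clear Test of Cure data counts as a cure for the assigned arm

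*Combined protocol and SAP*

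**What the plan says.** - **Missing outcomes (10.5.4, repeated in the synopsis).** "Missing data will be imputed as treatment failures for the primary and secondary efficacy analyses". The section then adds: "Missing data otherwise will not be imputed".
- **Endpoint (10.1.1).** Therapeutic cure is a negative culture plus absence of all signs and symptoms in the study ear at Test of Cure. No condition refers to other therapy.
- **Primary population (10.4.2).** "The MITT population will include subjects in the ITT population with a positive fungal culture at Screening/Baseline". Prohibited therapy is not a ground for exclusion.
- **Prohibited therapy (5.1.2).** For the treated ear: "Other than the study drug, no other topical medications" are allowed. For systemic treatment: "Other prohibited treatments include systemic antifungal therapy, warfarin, immunosuppressive or immune-stimulating drugs, and systemic steroids". No consequence for the efficacy outcome is given. The section describes one case, "A subject who discontinues study drug during the Randomization Period and who subsequently uses a topical corticosteroid", and settles only whether that subject may enter the open-label extension.
- **Per protocol set (10.4.3).** Subjects are removed if they "Used an interfering concomitant medication". This set is supportive, and the word interfering is not defined.
- **Sensitivity analyses (10.5.5).** A tipping point analysis in MITT and a repeat in the intent-to-treat (ITT) population, both introduced as exploring missing data.

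**The concern.** The plan is strict with a subject who misses the visit and silent on one who attends after using a product that can itself clear the culture or relieve itching. Under 4.3, use of a prohibited product is not a mandatory reason for discontinuation, so such a subject can stay in the study. There is also time for it to happen: dosing ends on Day 14 and the Test of Cure window runs to Day 22 + 8 = Day 30. Pruritus is scored over the previous 24 hours (7.4.1), so recent steroid use could bring it to zero.

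Few cures are expected on vehicle: 7.1% of 64 is about 4.5 subjects. Two or three cures that owe nothing to the assigned oil would change the comparison noticeably. If the text stays silent, the scoring of these subjects could also be settled after unblinding.

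**Working it through.** **1. The plan's own figure.** Inputs from 10.3: p1 = 0.250, p2 = 0.071, chi-square test, two-sided 0.05, 80% power. With pooled variance and mean rate 0.1605:

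n per arm = [1.960 × √(2 × 0.1605 × 0.8395) + 0.842 × √(0.250 × 0.750 + 0.071 × 0.929)]² / (0.179)² = (1.017 + 0.424)² / 0.03204 ≈ 64.8, rounded up to 65.

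That is 130 in total against the stated 128, so the figure reproduces. At 64 per arm the power is 79.5% by the normal approximation and 81.0% by exact enumeration of the uncorrected chi-square test. The exact figure is the baseline below. The sample size is not in dispute.

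**2. Who falls in the gap on the primary endpoint.**

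| Subject | Scored by the text as |
|---|---|
| Leaves early, no culture (not required: 4.3, 6.1.2.4, Table 3 note d) | Missing, so failure |
| Study ear has visible fungal elements at Test of Cure (as extension entry requires of at least one treated ear) | Fungal-elements score 1, so failure |
| Used prohibited therapy, attends, any sign or symptom above 0 or culture positive | Failure |
| Used prohibited therapy, attends, culture negative, all four scores 0 | **Cure for the assigned arm** |

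Only the last row is the problem.

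**3. Effect on power.** Let u be the share of an arm's subjects who would otherwise fail, use prohibited therapy and still have complete Test of Cure data. Let c be the chance that such a subject is scored cured. The observed rate is p + u × c. The documents give neither u nor c, so both are assumptions. Three values of c are shown: 8.3% (the Phase 2 cure rate after 7 days of miconazole, section 1.1), 25% (the rate after 14 days) and 50%.

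| Use, vehicle / miconazole | c = 8.3% | c = 25% | c = 50% |
|---|---|---|---|
| 5% / 0% | 25.0 vs 7.5: 78% | 25.0 vs 8.35: 73% | 25.0 vs 9.6: 64% |
| 5% / 2% | 25.2 vs 7.5: 79% | 25.5 vs 8.35: 75% | 26.0 vs 9.6: 69% |
| 10% / 0% | 25.0 vs 7.9: 76% | 25.0 vs 9.6: 64% | 25.0 vs 12.1: 47% |
| 10% / 5% | 25.4 vs 7.9: 77% | 26.25 vs 9.6: 70% | 27.5 vs 12.1: 59% |

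Each cell gives the observed rates (%) and the exact power at 64 per arm. In subjects, the worst cell is 64 × 0.10 × 0.50 = 3.2 extra vehicle cures. With equal use of 5% in both arms and c = 25%, power is 78%.

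**4. The opposite direction.** Suppose there is no true effect (7.1% in both arms), and 10% of would-be failures on miconazole and none on vehicle use such therapy. The miconazole rate becomes 0.071 + 0.929 × 0.10 × c. At c = 25% this is 9.4% and the exact rejection rate is 7.7%. At c = 50% it is 11.7% and the rejection rate is 14.6%. With no such use the rate is 5.0%.

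**The case against.** **Using observed outcomes regardless of other therapy is legitimate.** This stands as a choice of strategy. A reader might infer that therapeutic cure means cure by the assigned oil, but 10.1.1 defines it only by culture, signs and symptoms. What remains is that the protocol never states the choice, and places the silence beside a failure rule for missing data.

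**Section 5.1.2 does not show that outside antifungals are expected.** This stands. A reader might infer that the protocol foresees subjects moving to other otic antifungals. It foresees only a topical corticosteroid, for example for itching, and only to decide extension eligibility. A steroid alone would not be expected to clear the culture and remove fungal elements. Subjects who worsen and have visible fungal elements are also offered open-label miconazole after their final assessments, which reduces the need for outside treatment before then.

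**The large power losses rest on 50% of users being scored cured.** This stands. That is twice the 25.0% the sponsor saw after a full course of study drug. The 47-69% range is one end of an assumption and should not be read as the expected loss. The documents also do not say whether the Phase 2 rates already contain such cures; if they do, the 81% baseline already carries some dilution.

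**The bias only hurts the sponsor.** This does not stand. More use on vehicle is plausible: Phase 2 application site pruritus was 30.0% on vehicle and 18.2% on 14-day miconazole (Table 1), from groups of 20 and 22. Nothing fixes that direction, and the reverse inflates the false-positive rate.

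**The per protocol analysis covers it.** Only in part. It drops such subjects without scoring them, restores some who discontinued, and is supportive.

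**A rule may exist elsewhere.** Section 10 defers full detail to a separate statistical analysis plan whose text was not available for this review. If it has a rule, the protocol should match it.

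**Conclusion.** The concern holds in a limited form. As written, the primary MITT analysis credits a cure after prohibited therapy to the assigned arm whenever the Test of Cure data are complete and clear, and no planned sensitivity analysis examines this.

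Its size cannot be fixed from the documents. With 5-10% use on vehicle and 0-5% on miconazole, exact power falls from 81% to about 76-79% (8.3% of users cured), 64-75% (25%) or 47-69% (50%). If use is concentrated on miconazole, the null rejection rate is about 8-15% under the assumptions in step 4. The text does not support a claim that the trial is underpowered, that the bias must run against the drug, or that everyone who stops study drug and takes something else escapes the failure rule.

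**What to change.** Add to 10.5.4: an MITT subject who, between Day 1 and Test of Cure, received a non-study antifungal (systemic or in the study ear), a systemic steroid, or another prohibited topical product in the study ear judged interfering is a failure for therapeutic, clinical and mycological cure. Use the same flag as the per protocol criterion in 10.4.3, and fix the list of interfering products before unblinding, because 10.4.3 does not define the term. Limiting other topicals to those judged interfering avoids failing a subject for a trivial use. Add the as-observed result to 10.5.5 as a sensitivity analysis.

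If 25.0% and 7.1% are cure rates without such therapy, the rule keeps exact power at 81.0% with 128 subjects.

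**Cost.** A sentence or two and one derived flag; concomitant medications are already recorded at every visit. The downside is that miconazole subjects who used such therapy and were cured also become failures. This is a scoring rule only: it changes nothing about what subjects may receive or when treatment stops.
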